6.18.5.5. Elevations in Creatine Phosphokinase (CPK)

The planned summaries are provided in [Table JAHV.6.20](#) and are described more fully in compound-level safety standards.

Table JAHV.6.20. Summary Tables Related to Effects on CPK

Analysis
Shift tables showing the number and percentage of patients based on baseline to maximum will be created, with baseline depicted by the most extreme CTCAE grade during the baseline period. With each shift table, a summary displaying the number and percentage of patients who decreased, increased, or stayed the same in CTCAE grade category will be presented.
The number and percentages of patients with treatment-emergent shifts at any time will be summarized, based on any increase to CTCAE Grade 1 or above, Grade 2 or above, Grade 3 or above, and Grade 4 or above.
Treatment-emergent adverse events potentially related to muscle symptoms may also be analyzed based on reported AEs. The Muscle Symptoms special search category is a predefined MedDRA search criteria list that contains the narrow scope terms from the Rhabdomyolysis/myopathy SMQ (code 20000002) plus selected terms from the Musculoskeletal SOC

Abbreviations: AE = adverse event; CPK = creatine phosphokinase; CTCAE = Common Terminology Criteria for Adverse Events; MedDRA = Medical Dictionary for Regulatory Activities; PT = Preferred Term; SOC = System Organ Class.

6.18.5.6. Infections

Infections will be defined using all the PTs from the MedDRA Infections and Infestations System Organ Class (SOC). The MedDRA terms used to identify infections considered to be opportunistic infections (OIs) are based on Winthrop and colleagues (2015) and are listed in the compound-level safety standards. The list contains narrow (more specific) and broad (less specific) PTs.

The planned summaries are provided in [Table JAHV.6.21](#) and are described more fully in compound-level safety standards.

Table JAHV.6.21. Summary Tables Related to Infections

Analysis
The number and percentage of patients with treatment-emergent infections, serious infections, and infections resulting in permanent study drug discontinuation will be summarized using MedDRA PTs.
The number and percentage of patients with TEAEs of infections by maximum severity will be summarized using MedDRA PTs.
Listing of patients experiencing TEAE infections will be provided. The listing will include patient demographics, treatment group, treatment start and stop dates, infectious PT event, event start and stop dates, total leukocytes, total lymphocytes, absolute neutrophils, event seriousness, and event outcome.
Summary of Opportunistic Infections based on MedDRA PTs after the potential opportunistic infections are reviewed by medical and confirmed as opportunistic infections.
Listing of Opportunistic Infections based on MedDRA PTs during the study.
A summary table of herpes zoster will be provided, including event maximum severity, seriousness, whether resulting in temporary study drug interruption, whether resulting in study drug discontinuation, whether treated with antiviral medication, and event outcome.
The summary table of herpes simplex will include event maximum severity, seriousness, whether resulting in temporary study drug interruption, whether resulting in study drug discontinuation, and whether treated with antiviral medication.
A listing of patients with detectable HBV DNA will be provided.
Hepatitis B virus DNA status (not detectable, detectable but not quantifiable [ie, < lower limit of detection (LLOD)], quantifiable [ie, ≥LLOD]) will be summarized, stratified by applicable baseline HBV serology status.

Abbreviations: MedDRA = Medical Dictionary for Regulatory Activities; OI = opportunistic infection; PT = Preferred Term; TEAE = treatment-emergent adverse event; HBV = hepatitis B virus.

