Note: Temporary interruption rules (see Section 8.1.1) must be followed where applicable. For laboratory values that meet permanent discontinuation thresholds, investigational product should be discontinued. However, if in the opinion of the investigator the laboratory abnormality is due to intercurrent illness such as cholelithiasis or another identified factor, laboratory tests may be repeated. Only when the laboratory value meets resumption thresholds (Table JAHV.7) following the resolution of the intercurrent illness or other identified factor may the investigator restart investigational product after consultation with the Lilly-designated medical monitor.

In addition, patients will be discontinued from investigational product in the following circumstances:

- Pregnancy
- Malignancy
- HBV DNA detected with a value above limit of quantitation (see Section 9.4.4)
- Development of a VTE (DVT/PE) during the study

Patients discontinuing from the investigational product prematurely for any reason should complete follow up per Section 2 (Schedule of Activities), Section 9.2 (Adverse Events), and Section 9.4 (Safety).

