9.4.4. Hepatitis B Virus DNA Monitoring

Hepatitis B virus DNA testing will be performed in enrolled patients who tested positive for hBcAb at screening (refer to the Schedule of Activities in Section 2).

Patients who are hBcAb positive and HBV DNA negative (undetectable) at screening will require measurement of HBV DNA at Visit 9, Visit 12, Visit 15, Visit 17, ETV, and the follow-up visit, regardless of their hepatitis B surface antibody (hBsAb) status.

The following actions should be taken in response to HBV DNA test results:

- If a single result is obtained with a value “below limit of quantitation,” the test should be repeated within approximately 2 weeks.
- If the repeat test result is “target not detected,” monitoring will resume according to the study schedule.
- If the patient has 2 or more test results with a value “below limit of quantitation,” HBV DNA testing should be performed approximately once per month for the remainder of the study and referral to a hepatologist is recommended.
- If a result is obtained with a value above the limit of quantitation, at any time during the study, the patient will be permanently discontinued from investigational product (see Section 8.1.2) and should be referred to a hepatology specialist.
 - In selected cases, investigators may temporarily continue investigational product in accordance with current immunomodulator management in the setting of HBV DNA positivity. This option may be considered in consultation with Lilly (or its designee) and evaluation of individual patient risks and benefits.

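### The bracketed cut-points for HBV DNA status in SAP Table JAHV.6.21 use the limit of detection, which contradicts the row labels and does not match the protocol's limit-of-quantitation classes

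*SAP*

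**What the plan says.** **SAP.** Section 6.18.5.6, Table JAHV.6.21, summarises HBV DNA status by baseline serology in three classes. The first is not detectable, with no cut-point attached. The other two are "detectable but not quantifiable [ie, < lower limit of detection (LLOD)], quantifiable [ie, ≥LLOD". The limit is spelled out once and then used in both brackets. No quantitation limit is given. The row above in the same table adds a patient-level display: "A listing of patients with detectable HBV DNA will be provided". The section also says that its summaries "are described more fully in compound-level safety standards"; those standards are not among the documents.

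**Protocol.** Section 9.4.4 works with three result types, each with its own consequence:
- Target not detected on a repeat test: scheduled monitoring resumes.
- Below the limit of quantitation: after a single such result "the test should be repeated within approximately 2 weeks"; two or more lead to roughly monthly testing and a recommended hepatology referral.
- Above the limit: "If a result is obtained with a value above the limit of quantitation, at any time during the study", investigational product is permanently discontinued, with temporary continuation possible in selected cases.

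Section 8.1.2 lists the same trigger among the reasons for permanent discontinuation: "HBV DNA detected with a value above limit of quantitation".

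**The concern.** The SAP labels and the SAP brackets give two different rules. By label, the middle class holds results that are detected but cannot be quantified. By bracket, it holds results below the limit of detection, which the assay does not reliably detect and which overlap the not-detectable class. The bracket for the top class then admits anything from the limit of detection upwards, whether or not it can be quantified.

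The middle class is the one that should correspond to the protocol's retest results, and the top class is the one that should correspond to its discontinuation criterion. If the brackets decide, the top row can mix the two and the middle row can lose the results it was meant to show. Infections are an adverse event of special interest, and the protocol admits patients who are positive for hepatitis B core antibody and negative for HBV DNA on condition of added DNA monitoring. A reader of the clinical study report would look to this row to see how that monitoring turned out.

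**Working it through.** The plan states no figure to reproduce and no arithmetic applies. The check places a result r in each scheme.

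**Inputs.** The SAP labels and brackets come from Table JAHV.6.21; the protocol classes come from Sections 9.4.4 and 8.1.2. LLOD is the lower limit of detection and LLOQ the lower limit of quantitation. Neither document gives a value for either limit, so their order is an assumption.

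**Step 1. Take LLOD < LLOQ and results available as numbers.**

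| Result | Row by SAP label | Row by SAP bracket | Protocol class |
|---|---|---|---|
| r < LLOD, target not detected | not detectable | middle row, overlapping not detectable | target not detected |
| LLOD ≤ r < LLOQ | detectable but not quantifiable | quantifiable | below limit of quantitation |
| r > LLOQ | quantifiable | quantifiable | above limit of quantitation |

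Label and protocol agree in all three lines. The bracket agrees with them only in the last. In the second line it moves the result up one class, into the row that corresponds to the discontinuation criterion.

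**Step 2. Take LLOD = LLOQ.** No result can lie between the limits, so none moves up. The middle row still contradicts its own label, because its bracket describes results below the limit of detection.

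**Step 3. Take results that arrive as laboratory categories.** Section 9.4.4 puts two of its result types in quotation marks, which suggests reported categories. A result reported only as below the limit of quantitation has no number to compare with the LLOD, and the natural destination is the row whose label fits. Again none moves up.

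**Step 4. Size.** Among results between the two limits, the share counted one class too high is 100% under Step 1 with the brackets applied literally. It is 0% under Step 3, and under Step 2 there are no such results. The documents do not say which case applies.

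**Step 5. After the change.** With the cut at the LLOQ, the second line of the table moves to the middle row, and the three SAP rows line up with the three protocol classes. One edge remains: the protocol speaks of results below and above the limit, so a value exactly at the limit has no stated class there, while the SAP form uses at or above.

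**The case against.** The best defence is that the labels are right and show the intent. They correspond one to one with the protocol's classes, and the likeliest explanation is that LLOD was written where LLOQ was meant. A programmer would have to overlook a row named for exactly these results in order to put them elsewhere. The compound-level standards may also state the intended cut. This stands as a reason not to predict misclassification. It does not rescue the text: the brackets are offered as the definition of each label, so following one means setting the other aside, and standards outside the plan do not remove a conflict printed in it.

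The second defence is that little depends on this row. That largely stands. Retesting and discontinuation follow the protocol. The listing of detectable HBV DNA does not use the cut between the two limits. SAP Section 6.18 says listings will carry all safety data, and Section 6.6 plans a disposition listing with reasons for discontinuation. A reader might infer that the summary could not be reconciled with discontinuations under Sections 8.1.2 and 9.4.4. The documents do not support that, because patient-level reconciliation remains possible. Nor was the row ever an exact count of discontinuations, given the selected-case exception in Section 9.4.4. What remains is that a listing does not correct a wrong count in the summary.

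**Conclusion.** The bracketed definitions are wrong as written. They contradict their own labels whatever the assay limits are, and they do not match the classes in protocol Sections 9.4.4 and 8.1.2. The consequence is conditional. Results between the limits are counted as quantifiable only if the brackets are applied literally, the LLOD is below the LLOQ, and low-level results are held as numbers. The range is 0% to 100% of such results.

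Two stronger readings are tempting. A reader might infer that all detected but unquantifiable results will be tabulated as quantifiable; that needs assay limits and a reporting format that the documents do not give. A reader might also infer that one or two results would change the whole table; neither document gives an expected number of core-antibody-positive patients, so this cannot be shown. The effect is confined to one descriptive safety summary. No efficacy result and no patient's management depends on it.

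**What to change.** In Table JAHV.6.21, replace LLOD with the lower limit of quantitation in both brackets, so that the classes read: target not detected; detected but < LLOQ; quantifiable, ≥ LLOQ. Name the laboratory's LLOQ for the assay, or state that its reported result categories will be used directly. Reconcile the boundary wording with protocol Section 9.4.4, which refers to values above the limit, so that a result exactly at the limit has one agreed class in both documents. If the compound-level safety standards carry the same brackets, correct them there too.

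The cost is one line of SAP text and, where numeric values are used, one programming threshold. No new data are needed.

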6.18.5.7. Allergic Reactions and Hypersensitivities

A search for relevant events related to allergic reaction and hypersensitivity will be performed using the following SMQs:

- Anaphylactic reaction SMQ (20000021)
- Hypersensitivity SMQ (20000214)
- Angioedema SMQ (20000024)

Events that satisfy the queries will be listed, by temporal order within patient ID, and will include SOC, PT, SMQ event categorization including detail on the scope (narrow or broad), reported AE term, AE onset and end dates, severity, seriousness, outcome, etc.

The summaries described in [Table JAHV.6.22](#) will be created if there are sufficient numbers of events to warrant further examination beyond the listing specified above.

The anaphylactic reaction SMQ consists of a narrow search containing PTs that represent core anaphylactic reaction terms, a broad search that contains additional terms (signs and symptoms

possibly indicative of anaphylactic reaction) that are added to those included in the narrow search, and an algorithm.

The algorithmic approach (Algorithm 1) (which is similar to the algorithm approach defined in Sampson, et al 2006) comprises 1 or more events associated with an individual administration of study drug, where the events include:

- A narrow term from the anaphylactic reaction SMQ (Category A of the SMQ) or
- Paired terms from the anaphylactic reaction SMQ, comprising terms from at least 2 of the following 3 categories from the SMQ:
 - o Category B - (Upper Airway/Respiratory signs and symptoms)
 - o Category C - (Angioedema/Urticaria/Pruritus/Flush signs and symptoms)
 - o Category D - (Cardiovascular/Hypotension signs and symptoms).

Within the paired terms approach, it is important to recognize that occurrence of these events should be nearly coincident and develop rapidly after exposure to an antigen; a window wherein onset or severity change of the events occur within the same calendar day will be used.

In addition, a second algorithmic approach (Algorithm 2) will be calculated similarly to the algorithm approach defined above (Algorithm 1) but includes an additional category, Category E. The paired terms according to Algorithm 2 will comprise terms from at least 2 of 4 categories (Categories B, C, D, and E). Categories B, C and D are already defined, and Category E includes any of the Gastrointestinal preferred term events (Nausea, Vomiting, Diarrhoea, and Abdominal pain). A patient's listing will be generated based on Algorithm 2 and individual cases will be examined to determine if the cases suggest anaphylaxis. Those cases suggestive of anaphylaxis will be described in CSR.

Table JAHV.6.22. Summary Tables Related to Allergic Reactions/Hypersensitivities

Analysis
Two listings for Allergic Reaction and Hypersensitivities for events that satisfy the queries defined in this section will be listed, by temporal order within patient ID, and will include SOC, PT, SMQ event categorization including detail on the scope (narrow, algorithmic, or broad), reported AE term, AE onset and end dates, severity, seriousness, outcome, etc.
The number and percentages of patients with TEAEs will be summarized using MedDRA Preferred Term for any narrow or algorithmic term in the compound-level safety standard from any one of the 3 SMQs (each SMQ and SMQs combined)
The number and percentages of patients with TEAEs will be summarized using MedDRA Preferred Term for any broad term (each SMQ separately)

Abbreviations: MedDRA = Medical Dictionary for Regulatory Activities; SMQ = Standardised MedDRA Query; TEAE = treatment-emergent adverse event.

6.18.5.8. Major Adverse Cardiovascular Events and Other Cardiovascular Events

Major Adverse Cardiovascular Events (MACE) and other cardiovascular events will be adjudicated by an independent, external adjudication committee. All confirmed events after adjudication will be used for the analysis.

The planned summaries are provided in [Table JAHV.6.23](#) and are described more fully in compound-level safety standards.

Table JAHV.6.23. Summary Tables Related to MACE and Other Cardiovascular Events

Analysis
The number and percentage of patients with MACE, other cardiovascular events, non-cardiovascular death, and all-cause death, as positively adjudicated , will be summarized based on the categories and subcategories as defined in compound-level safety standards.
A listing of the MACE and other CV events sent for cardiovascular adjudication will be provided to include data concerning the MedDRA PT related to the event, the seriousness of the event, and the event outcome, along with the adjudicated result.

Abbreviations: MACE = Major Adverse Cardiovascular Event; MedDRA = Medical Dictionary for Regulatory Activities; PT = Preferred Term.

6.18.5.9. Thromboembolic Events

Venous thromboembolic (VTE) events will be adjudicated by an independent, external adjudication committee. Venous and pulmonary artery thromboembolic events will be classified as deep vein thrombosis (DVT), pulmonary embolism (PE), or other peripheral venous thrombosis. Additionally, arterial thromboembolic (ATE) events will be adjudicated by an independent, external adjudication committee. All confirmed events after adjudication will be used for the analysis.

The planned summaries for VTE are provided in [Table JAHV.6.24](#) and are described more fully in compound-level safety standards.

Table JAHV.6.24. Summary of Tables Related to VTE Events

Analysis
The number and percentage of patients with a VTE, DVT/PE, DVT, PE, and other peripheral venous thrombosis, as positively adjudicated, will be summarized
A listing of the VTEs sent for adjudication will be provided to include data concerning the MedDRA PT related to the event, the seriousness of the event, and the event outcome, along with the adjudicated result.

Summary of Tables Related to VTE Events

Abbreviations: DVT = deep vein thrombosis; MedDRA = Medical Dictionary for Regulatory Activities; PE = pulmonary embolism; PT = Preferred Term; VTE = venous thromboembolic.

Arterial Thrombosis(ATE) Events

The planned summaries for ATE are provided in [Table JAHV.6.25](#) and are described more fully in compound-level safety standards.

Table JAHV.6.25. Summary of Tables Related to ATE Events

Analysis
The number and percentage of patients with a positively adjudicated ATE
A listing of the ATEs sent for adjudication to include data concerning the MedDRA PT related to the event, the seriousness of the event, and the event outcome, along with the adjudicated result

Abbreviations: ATE = arterial thromboembolic; MedDRA = Medical Dictionary for Regulatory Activities; PT = preferred term; VTE = venous thromboembolism.

6.18.5.10. Malignancies

Malignancies will be identified using terms from the Malignant tumors SMQ. Malignancies excluding nonmelanoma skin cancers (NMSC) and NMSC will be reported separately. All the cases identified by the Malignant tumors SMQ (SMQ code = 20000194) will be assessed through medical review to determine *confirmed* NMSC cases.

The planned summaries are provided in [Table JAHV.6.26](#) and are described more fully in compound-level safety standards.

Table JAHV.6.26. Summary Tables Related to Malignancies

Analysis
The number and percentage of patients with treatment-emergent malignancies excluding NMSC and NMSC will be summarized.
Listing of all malignancy cases, with an NMSC flag.

Abbreviations: NMSC = nonmelanoma skin cancers.

6.18.5.11. Gastrointestinal Perforations

Potential gastrointestinal (GI) perforations will be identified using terms from the GI perforations SMQ. Potential GI perforations identified by the SMQ (SMQ code = 20000107) search will be provided as a listing for internal review by the medical safety team. Each case will be assessed to determine whether it is a GI perforation. All confirmed events after medical review will be used

for the analysis. The planned summaries are provided in [Table JAHV.6.27](#) and are described more fully in compound-level safety standards.

Table JAHV.6.27. Summary Tables Related to Gastrointestinal Perforations

Analysis
The number and percentage of patients with treatment-emergent gastrointestinal perforations will be summarized using MedDRA PTs.
Listing of all treatment-emergent gastrointestinal perforations during the study.

Abbreviations: MedDRA = Medical Dictionary for Regulatory Activities; PT = Preferred Term.

6.19. COVID-19 Trial Impact

Patients who experience an impact to their trial participation due to quarantine and/or travel restrictions related to COVID-19 will have their type of impact summarized. COVID-19 specific impacts will be summarized by the following by-patient listings:

- Listing of study and treatment discontinuation related to COVID-19
- Listing of COVID-19 adverse events based on SMQ=20000237 using the narrow term classification.
- Summary of COVID-19 TEAE using MedDRA PT based on SMQ=20000237 with the narrow term classification

6.20. Protocol Deviations

Protocol deviations will be tracked by the clinical team, and their importance will be assessed by key team members during protocol deviation review meetings. Out of all protocol deviations identified, a subset occurring during the OLLI prior to the Week 12 with the potential to affect futility analyses, will result in exclusion from futility analysis.

Potential examples of protocol deviations include patients who receive excluded concomitant therapy, significant noncompliance with study medication, patients incorrectly enrolled in the study, and patients whose data are questionable due to significant site quality or compliance issues.

Refer to a separate document for the important protocol deviations.

The number and percentage of patients having IPD(s) will be summarized in the OLLI and the DBW periods (by treatment) within category and subcategory of deviation using the OLLI and DBW populations. Individual patient listings of IPDs will be provided. A summary of reasons patients were excluded from the futility analysis will be provided.

